## 7.5 Efficacy

Analyses in this section will be tabulated for all randomized subjects by treatment group as randomized, unless otherwise specified.

CI for all efficacy endpoints will be at the two-sided 95% level and two-sided 90% level. Point estimates and confidence bounds for efficacy variables will be rounded to the second decimal place.

- A by-subject listing of efficacy results will be presented including treatment group, planned and actual surgery type, RCB, pCR, ORR, death date, etc.

### 7.5.1 Analysis of Residual Cancer Burden (RCB)

The primary objective of the Randomized phase of the study is to estimate the RCB 0-I rate per central assessment in the treatment groups among all randomized subjects.

The number and percentage of subjects in each category of RCB per central assessment (0, I, II, III) will be presented, by treatment group. Estimates of RCB 0-I rate along with its exact two-sided 95% and two-sided 90% CI by Clopper and Pearson will be presented, by treatment group.

- A by-subject listing of RCB will be presented including treatment group, RCB, randomization date, surgery date [REDACTED].

### 7.5.2 Analysis of Pathological Complete Response (pCR)

One of the secondary objectives of the study is to estimate the pCR rate per local assessment in the treatment groups among all randomized subjects.

The number and percentage of subjects in each category of pathological response per local assessment (pCR, non-pCR) will be presented, by treatment group. Estimates of pCR rate along with its exact two-sided 95% CI by Clopper and Pearson will be presented, by treatment group.

- A by-subject listing of pCR will be presented including treatment group, pCR, randomization date, surgery date [REDACTED].

### 7.5.3 Analysis of Breast-Conserving Surgery (BCS) Rate

One of the secondary objectives of the study is to estimate the BCS rate in the treatment groups among all randomized subjects.

The number and percentage of subjects in each category of planned surgery (breast-conserving, mastectomy) and actual surgery (breast-conserving, mastectomy) will be presented, by treatment group. BCS rate is defined as the number of participants who actually undergo BCS after completing the study treatment divided by the number of all randomized participants in each treatment group. Estimates of BCS rate along with its exact two-sided 95% CI by Clopper and Pearson will be presented, by treatment group.

- A by-subject listing of planned and actual surgery will be presented including treatment group, randomization date, planned surgery type, actual surgery type, surgery date [REDACTED].

[figure not shown]
#### **7.5.4 Analysis of Objective Response Rate (ORR)**

One of the secondary objectives of the study is to estimate the ORR per investigator radiographic assessment in the treatment groups among all randomized subjects.

The number and percentage of subjects in each category of BOR per investigator assessment (complete response [CR], partial response [PR], stable disease [SD], progressive disease [PD], or not evaluable [NE]) will be presented, by treatment group. Estimates of response rate, along with its exact two-sided 95% and two-sided 90% CI by Clopper and Pearson will be presented, by treatment group.

- A by-subject listing of best overall response will be presented including treatment group, best overall response and dates of CR/PR/progression.
- A by-subject, by-visit, by-lesion listing of tumor assessment will be presented.

Similar analyses will be repeated based on the investigator clinical assessment of ORR. A by-subject listing of per time point tumor response per clinical assessment will be presented.

## **7.6 Safety**

Analyses in this section will be tabulated for all treated subjects by treatment group as treated, unless otherwise specified.

### **7.6.1 Dose Limiting Toxicities (Safety Run-In Phase)**

Dose limiting toxicities will be summarized by cohort and dose level. A corresponding by-subject listing will be provided for all treated subjects.

### **7.6.2 Deaths**

Deaths will be summarized by treatment group:

- All deaths, reasons for death.
- Deaths within 30 days of last dose received, reasons for death.
- Deaths within 100 days of last dose received, reasons for death.

A by-subject listing of deaths will be provided for all enrolled subjects population.

### **7.6.3 Serious Adverse Events**

Serious adverse events will be summarized by treatment group:

- Overall summary of SAEs by worst CTC grade (any grade, grade 3-4, grade 5) presented by SOC/PT.
- Overall summary of drug-related SAEs by worst CTC grade (any grade, grade 3-4, grade 5) presented by SOC/PT.
- All analyses will be conducted using the 30-day safety window.

A by-subject SAE listing will be provided for the “enrolled subjects” population.

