[figure not shown]
In the Randomized Phase, participants will be randomly assigned by an IRT system to 3 different treatment arms and stratified by the following factors:

2) evaluation of lymph nodes (cytologically positive vs radiologically or cytologically negative); and 3) tumor size (> 3 cm or ≤ 3 cm).

For both the Safety Run-in Phase and Randomized Phase, participants will be treated for a maximum of 5 cycles (1 cycle = 4 weeks). Participants with progressive disease prior to completion of the 5-cycle study treatment must discontinue all study drugs and proceed to the Safety Follow-up Period. Participants who permanently discontinue the study drugs for any reason are considered to have completed the On-treatment Pre-surgery (neoadjuvant) Period, and hence reach end of treatment (EOT). After Cycle 5 or EOT, participants must continue to receive anastrozole (as concomitant medication and not as study treatment) until subsequent SOC breast surgery. Following the completion of neoadjuvant treatment, all participants who remain operative candidates will undergo definitive surgery for BC within 4 weeks of the last neoadjuvant treatment administration. If anastrozole can no longer be administered after EOT, participants will go to breast surgery right away. Pre-surgical lymph node biopsy is not allowed. Information on the type of the surgery will be collected and recorded in the electronic case report form (eCRF). Surgical specimens will be collected for the analyses outlined in the protocol. Depending on treatment assignment, up to 2 safety follow-up visits will be conducted in person. The first safety follow-up visit (FU1) will be completed for all participants within 30 days (± 7 days) from the last study treatment (oral or intravenous [IV], whichever occurs later). The second safety follow-up visit (FU2) will occur approximately within 100 days (± 7 days) from the last dose of nivolumab and will be required for participants in the Safety Run-in Phase and participants randomized to Arms A or B in the Randomized Phase. Further planned treatment of participants in the adjuvant setting (ie, radiotherapy, endocrine treatment, chemotherapy or any other treatment modality) will be at the discretion of the treating physician, following local clinical guidelines, and collected in the appropriate eCRF.

The study design schematic is presented in [Figure 5.1-1](#).

Figure 5.1-1: Study Design Schematic

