9.2.1 Time Period and Frequency for Collecting AE and SAE Information

Sections 5.6.1 and 5.6.2 in the IB represent the Reference Safety Information to determine expectedness of SAEs for expedited reporting.

All SAEs must be collected from the time of signing the consent, including those thought to be associated with protocol-specified procedures and for a minimum of 100 days of discontinuation of nivolumab dosing. For participants randomized in Arm C, SAEs should be collected for 30 days from the date of last dose. For participants randomized/assigned to treatment and never treated with study drug, SAEs should be collected for 30 days from the date of randomization/treatment assignment.

The Investigator must report any SAE that occurs after these time periods and that is believed to be related to study drug or protocol-specified procedure (eg, a follow-up skin biopsy).

- Medical occurrences that begin before the start of study treatment but after obtaining informed consent will be recorded on the appropriate section of the eCRF module.
- All SAEs will be recorded and reported to the Sponsor or designee within 24 hours, as indicated in [Appendix 3](#).
- The Investigator will submit any updated SAE data to the Sponsor or designee within 24 hours of updated information being available.

Investigators are not obligated to actively seek AEs or SAEs in former study participants. However, if the Investigator learns of any SAE, including a death, at any time after a participant has been discharged from the study, and he/she considers the event reasonably related to the study treatment or study participation, the Investigator must promptly notify the Sponsor.

The method of evaluating, and assessing causality of AEs and SAEs and the procedures for completing and reporting/transmitting SAE reports are provided in [Appendix 3](#).

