9.2.2 Method of Detecting AEs and SAEs

AEs can be spontaneously reported or elicited during open-ended questioning, examination, or evaluation of a participant. Care should be taken not to introduce bias when collecting AEs and/or SAEs. Inquiry about specific AEs should be guided by clinical judgement in the context of known AEs, when appropriate for the program or protocol.

All non-serious AEs (not only those deemed to be treatment-related) should be collected continuously during the On-treatment Pre-surgery (neoadjuvant) Period and for a minimum of 100 days following discontinuation of nivolumab. For participants randomized in Arm C, non-serious AEs should be collected for 30 days from the date of last dose.

Every AE must be assessed by the Investigator with regard to whether it is considered immune-mediated. For events which are potentially immune-mediated, additional information will be collected on the participant's eCRF.

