## 6 STUDY PERIODS, TREATMENT REGIMENS AND POPULATIONS FOR ANALYSES

### 6.1 Study Periods

- Baseline period:
  - Baseline evaluations or pre-treatment events will be defined as evaluations or events that occur before the date and time of the first dose of study treatment. Evaluations (laboratory tests, pulse oximetry, vital signs [REDACTED]) on the same date and time of the first dose of study treatment will be considered as baseline evaluations. Events (AEs) on the same date and time of the first dose of study treatment will not be considered as pre-treatment events.
  - In cases where the time (onset time of event or evaluation time and dosing time) is missing or not collected, the following definitions will apply:
    - ◆ Pre-treatment AEs will be defined as AEs with an onset date prior to but not including the day of the first dose of study treatment;
    - ◆ Baseline evaluations (laboratory tests, pulse oximetry, vital signs [REDACTED]) will be defined as evaluations with a date (and time if collected) on or prior to the date of first dose of study treatment.
  - If there are multiple valid observations in the baseline period, then the latest non missing observation will be used as the baseline in the analyses. If multiple observations exist on the latest collection date (and time if collected), the record with the latest data entry date and time will be used. If multiple observations exist on the latest collection date (and time if collected) and data entry date and time, then the first observation is used as baseline, unless otherwise specified.

- ◆ Refer to the study-specific protocol for potential additional baseline evaluations definition such as baseline tumor evaluation, etc.
- Post baseline period:
  - On-treatment AEs will be defined as AEs with an onset date and time on or after the date and time of the first dose of study treatment (or with an onset date on or after the day of

first dose of study treatment if time is not collected or is missing). For subjects who are off study treatment, AEs will be included if event occurred within a safety window of 30 days (or 100 days depending on the analysis) after the last dose of study treatment. No “subtracting rule” will be applied when an AE occurs both pre-treatment and post-treatment with the same preferred term and grade.

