### **7.6.4 Adverse Events Leading to Discontinuation of Study Therapy**

AEs leading to discontinuation will be summarized by treatment group:

- Overall summary of AEs leading to discontinuation by worst CTC grade (any grade, grade 3-4, grade 5) presented by SOC/PT.
- Overall summary of drug-related AEs leading to discontinuation by worst CTC grade (any grade, grade 3-4, grade 5) presented by SOC/PT.

The analyses will be conducted using the 30-day safety window.

A by-subject AEs leading to discontinuation listing will be provided.

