### **7.6.6 Adverse Events**

Adverse events will be summarized by treatment group.

The following analyses will be conducted using the 30 days safety window only:

- Overall summary of any AEs by worst CTC grade (1, 2, 3, 4, 5, not reported, total) presented by SOC/PT.
- Overall summary of any AEs presented by worst CTC grade (any grade, grade 3-4, grade 5) by SOC/PT. This table will be restricted to events with an incidence greater or equal to 5% in any treatment group.
- Overall summary of any non-serious AEs presented by SOC/PT. This table will be restricted to events with an incidence greater or equal to 5% in any treatment group.
- Overall summary of any AEs that required immune modulating medication by worst CTC grade (any grade, grade 3-4, grade 5) presented by SOC/PT.
- Overall summary of drug-related AEs by worst CTC grade (1, 2, 3, 4, 5, not reported, total) presented by SOC/PT.

The following analyses will be conducted using the 30 days safety window and repeated using the 100 days safety window:

- Overall summary of drug-related AEs by worst CTC grade (any grade, grade 3-4, grade 5) presented by SOC/PT.

A by-subject AE listing will be provided. A by-subject listing of any AE requiring immune modulating medications will also be provided.

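### No SAE table runs past 30 days after last study treatment, although SAEs in the run-in and Arms A and B are collected for at least 100 days after nivolumab

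*SAP*

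**What the plan says.** - SAE incidence is a named secondary safety endpoint (Protocol 4, Table 4-1; SAP 4.2.4).
- Protocol 9.2.1 collects SAEs from consent and "for a minimum of 100 days of discontinuation of nivolumab dosing". The control arm differs: "For participants randomized in Arm C, SAEs should be collected for 30 days from the date of last dose". Protocol 9.2.2 sets the same pattern for non-serious events, "for a minimum of 100 days following discontinuation of nivolumab" in the nivolumab groups and 30 days in Arm C.
- SAP 6.1 counts an event in someone off treatment if it falls "within a safety window of 30 days (or 100 days depending on the analysis) after the last dose of study treatment". The anchor is the last dose of any study drug, not the last infusion.
- SAP 7.6.3 plans an all-cause and a drug-related SAE table and says: "All analyses will be conducted using the 30-day safety window". It adds a by-subject SAE listing for all enrolled subjects, with no window stated. The serious select-AE tables in SAP 7.6.7.1 are also 30-day only.
- Elsewhere the SAP does go to 100 days. For drug-related AEs by grade, 7.6.6 says: "The following analyses will be conducted using the 30 days safety window and repeated using the 100 days safety window". Deaths (7.6.2), immune-mediated AEs (7.6.8), other events of special interest (7.6.9) and ILD/pneumonitis (7.6.10) also have 100-day tables.
- Under Protocol 5.1, participants who remain operable "will undergo definitive surgery for BC within 4 weeks of the last neoadjuvant treatment administration".

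**The concern.** The trial asks whether adding nivolumab to palbociclib and anastrozole before surgery is safe and effective. Two kinds of serious event bear on that: delayed immune toxicity and complications around the operation. Both can arise after the 30-day window has closed, and the protocol collects them. The SAP accepts elsewhere that late events matter, since it repeats or places several safety tables at 100 days, but it does not do so for the SAE endpoint itself. A reader who takes the SAE rate from the summary table would therefore get a figure that omits a sizeable part of the collected follow-up in the nivolumab groups. The remaining SAEs would have to be counted by hand from a listing.

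**Working it through.** The plan gives no figure of its own to reproduce. The check is a day count, followed by a comparison of tables.

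**Inputs.** Cycles are 28 days and there are five (Protocol 5.1). In the run-in and in Arms A and B the last planned infusion is Cycle 5 Day 1 (Protocol 7.1). Anastrozole is taken daily and stops being study treatment at the end of Cycle 5 (Protocol 7.1, table footnotes). The table window is 30 days from last study treatment (SAP 6.1, 7.6.3). Minimum SAE collection is 100 days from last nivolumab (Protocol 9.2.1). Surgery is due within 4 weeks of the last dose (Protocol 5.1).

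**Participant who completes Cycle 5**

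- Last nivolumab: 4 × 28 + 1 = Day 113
- Last study drug: 5 × 28 = Day 140
- SAE table closes: 140 + 30 = Day 170, which is 170 − 113 = 57 days after nivolumab
- Minimum collection ends: 113 + 100 = Day 213
- Collected but outside the table: 213 − 170 = 43 of 100 days

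**General form.** Let L be the days from last nivolumab to last study drug. The table closes at L + 30, so the gap is 100 − (L + 30) = 70 − L.

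- L = 27 (completer): 43 days
- L = 20: 50 days
- L = 0 (all drugs stopped on a nivolumab day, an assumed extreme): 70 days
- L = 27 + 28 = 55 (Cycle 5 infusion omitted, oral drugs continued): 15 days

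**Post-operative time, completer.** Let surgery fall s days after last dose, with s from 1 to 28 assumed. Days in the table are 30 − s. Days collected are 100 − (27 + s) = 73 − s.

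| s | In SAE table | Collected | Share |
|---|---|---|---|
| 1 | 29 | 72 | 40% |
| 7 | 23 | 66 | 35% |
| 14 | 16 | 59 | 27% |
| 21 | 9 | 52 | 17% |
| 28 | 2 | 45 | 4% |

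With L = 0 the shares are lower, from 29 of 99 (29%) to 2 of 72 (3%). If the Cycle 5 infusion was omitted (L = 55) and surgery is prompt, the balance reverses: at s = 1, 29 of 100 − 56 = 44 days are covered. The statement that most post-operative time is outside is therefore for participants who received the Cycle 5 infusion or stopped all drugs earlier.

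**Where a serious event goes after the 30-day window**

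| Event | 100-day table | Serious events shown separately? |
|---|---|---|
| Fatal | Deaths, 7.6.2 | By cause of death |
| Judged drug-related | 7.6.6, by term and grade | No |
| Immune-mediated category (non-endocrine only if given immune-modulating medication, 7.1.1.3) | 7.6.8 | No |
| Listed special-interest term | 7.6.9 | No |
| ILD or pneumonitis | 7.6.10 | No |
| Non-fatal, judged unrelated, outside the listed terms | None by grade or seriousness | No |

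The last row may still be counted in the exposure-adjusted table of all AEs (7.6.11), because SAP 7.1.1 runs exposure to 100 days in the nivolumab groups. That table has no grade or seriousness split, describes its events only as on-treatment, and gives occurrences and rates rather than participants with an SAE.

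**The case against.** The strongest defence is that 30 days is the only window common to all three arms, because Arm C is collected no further. Beyond it, all-cause SAEs mix with the effects of surgery, radiotherapy and chemotherapy. Keeping all-cause SAEs at 30 days and showing drug-related and immune events at 100 days is a coherent scheme. The SAE listing has no stated window, and with about 115 to 136 treated participants it can be read. All of this stands as a reason to keep the 30-day tables. It does not explain why drug-related SAEs stop at 30 days when drug-related AEs do not, and a listing gives no incidence for a named endpoint.

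Three stronger readings are tempting and are not supported:

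- *Late immune or post-surgical serious events never reach a summary table.* Late immune and drug-related events appear in the 100-day tables shown above, and an event with missing relatedness is treated as related (SAP 7.1.1). Deaths are tabulated to 100 days and overall. What is lost for these events is the serious classification, not the event.
- *Most post-surgical serious events are missed.* The arithmetic counts days, not events, and the documents give no event timing. Surgery soon after the last dose leaves up to 29 post-operative days inside the window. Admission for a planned protocol procedure is not itself an SAE (Protocol Appendix 3).
- *SAP 7.6.4 needs the same change.* It too says "The analyses will be conducted using the 30-day safety window", for AEs leading to discontinuation. Such an event is defined by the drug having been stopped, so it normally begins before or near the last dose, and discontinuing nivolumab stops all study treatment (Protocol 8.1.1). Immune-mediated AEs leading to discontinuation are already tabulated at 100 days (SAP 7.6.8). A repeat would add almost nothing.

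**Conclusion.** The point holds in a limited form: SAP 7.6.3 leaves part of the collected SAE follow-up in the run-in and Arms A and B without any SAE table. The gap is 43 of 100 days for a participant who receives the Cycle 5 infusion and takes anastrozole to Cycle 5 Day 28. It reaches 70 days at the early-stopping extreme and is shorter where late infusions were omitted. The substantive loss is twofold: SAE incidence as such, and any graded incidence of late non-fatal serious events judged unrelated and outside the listed terms, with surgical complications the obvious example. No share of events can be derived. Arm C has no gap, because its SAE collection and its table window both end at 30 days. This is an inexpensive improvement to reporting, not a failure of safety data capture.

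**What to change.** In SAP 7.6.3:

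- Keep the 30-day SAE and drug-related SAE tables as the between-arm view.
- Repeat both with the 100-day window for the run-in and Arms A and B.
- State the anchor. Counted from last study treatment, as in SAP 6.1, the window for a completer ends on 140 + 100 = Day 240. Minimum collection runs from nivolumab and ends on Day 213, so the last 27 days would rest on reporting beyond the required minimum. Counted from last nivolumab, the window matches collection.
- Footnote that Arm C is collected to 30 days only, so there is no like-for-like column, and that the later window includes events from surgery and adjuvant therapy.

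SAP 7.6.4 can stay as it is. The cost is two repeat tables from data already collected, with no change to visits or case report forms. The small downside is that the 100-day figures cannot be compared with Arm C and carry some events due to later treatment, which the footnote makes plain.

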### **7.6.4 Adverse Events Leading to Discontinuation of Study Therapy**

AEs leading to discontinuation will be summarized by treatment group:

- Overall summary of AEs leading to discontinuation by worst CTC grade (any grade, grade 3-4, grade 5) presented by SOC/PT.
- Overall summary of drug-related AEs leading to discontinuation by worst CTC grade (any grade, grade 3-4, grade 5) presented by SOC/PT.

The analyses will be conducted using the 30-day safety window.

A by-subject AEs leading to discontinuation listing will be provided.

### **7.6.5 Adverse Events Leading to Dose Modification**

AEs leading to dose delay/reduction will be summarized by treatment group:

- Overall summary of AEs leading to dose delay/reduction by worst CTC grade (any grade, grade 3-4, grade 5) presented by SOC/PT.
- Overall summary of related AEs leading to dose delay/reduction by worst CTC grade (any grade, grade 3-4, grade 5) presented by SOC/PT.

The analysis will be conducted using the 30-day safety window.

A by-subject AEs leading to dose delay/reduction listing will be provided.

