9.2.9 Management Algorithms for Nivolumab

IO agents are associated with IMAEs that can differ in severity and duration from AEs caused by other therapeutic classes. Nivolumab is considered an IO agent in this protocol. Early recognition and management of IMAEs associated with IO agents may mitigate severe toxicity. Management algorithms have been developed from extensive experience with nivolumab to assist Investigators in assessing and managing the following groups of IMAEs:

- GI
- Renal
- Pulmonary
- Hepatic
- Endocrinopathies

- Skin
- Neurological
- Myocarditis

The algorithms recommended for the management of IMAEs in this protocol are in [Appendix 6](#). Please note that for this protocol, nivolumab delay means nivolumab omission.

- Checkpoint inhibitor molecules have been uncommonly associated with ocular drug-related AEs. Inflammation of components within the eye (eg, episcleritis, uveitis) are uncommon events of nivolumab monotherapy (< 1% of cases). These events are usually of low or intermediate grade, reversible, detected early in the course of therapy, and manageable with topical or systemic steroids.
 - Routine eye examinations should be performed in participants receiving immune checkpoint inhibitors ([Section 2](#) [Schedule of Activities]). Upon clinical suspicion of an ocular event consider ophthalmic consult, dose omission, or dose discontinuation.
 - Permanently discontinue for clinically significant or severe immune-mediated adverse reactions. Initiate systemic corticosteroids for severe immune-mediated adverse reactions.
 - Permanently discontinue for immune-mediated ocular disease that is unresponsive to local immunosuppressive therapy.
 - Administer corticosteroid eye drops to participants who develop uveitis, iritis, or episcleritis.

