### **7.1.1 Adverse Events, Serious Adverse Events, Multiple events, and Immune-Mediated Adverse Events**

Drug-related AEs are those events with relationship to study drug “Related”, as recorded on the CRF. If the relationship to study drug is missing, the AE will be considered as drug-related.

Serious adverse events consist of AEs deemed serious by the Investigator and flagged accordingly in the CRF and clinical database.

Adverse events leading to study drug discontinuation are AEs with action taken regarding study drug(s) = “Drug was discontinued”.

Adverse events that led to dose interruption of the drug will be coded with action “Drug was interrupted”.

Adverse events that led to dose omission of the drug will be coded with action “Dose was omitted”.

Adverse events leading to dose reduction are AEs with action taken regarding study drug(s) = “Dose was reduced”.

Adverse events will be coded using the Medical Dictionary for Regulatory Activities (MedDRA), and the most recent version of the dictionary at the time of the database lock will be used. Adverse event results will be graded for severity using the NCI Common Terminology Criteria for Adverse Events (CTCAE) and the version of the criteria specified in the protocol will be used.

In the AE summary tables, unless otherwise specified, subjects will be counted only once at the Preferred Term (PT), only once at the System Organ Class (SOC), and only once at subject level for the counting of total number of subjects with an AE. The AE tables will be sorted by the SOCs and then PTs. SOC will be ordered by descending frequency overall and then alphabetically. PTs will be ordered within SOC by descending frequency overall and then alphabetically. The sorting will be done based on the ‘Any Grade’ column of the experimental arm when arms are presented side-by-side.

Unless otherwise specified, the AE summary tables will be restricted to on-treatment events regardless of the causality.

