### 7.4.2 Modifications of Study Therapy

Participants are to start nivolumab within 3 calendar days of randomization. Participants will receive nivolumab at a dose of 480 mg as a 30-minute IV infusion for a maximum of 5 cycles (maximum 4 cycles for Arm B). Doses of nivolumab may be interrupted, omitted, or discontinued, depending on how well the participant tolerates the treatment. There will be no dose escalations or reductions of nivolumab allowed. For Q4W dosing cycles, participants may be dosed within a ± 3-day window. If a participant cannot receive nivolumab within a ± 3-day window, nivolumab must be omitted (skipped) for that cycle. If nivolumab is omitted, the other study medications may continue. If a participant discontinues nivolumab, the entire study treatment (CDK4/6 inhibitor

and anastrozole) must be discontinued. When nivolumab is scheduled to be administered on the same day with palbociclib plus anastrozole, nivolumab dosing should be started > 1 hour after palbociclib plus anastrozole ingestion. If nivolumab cannot be given within 3 days of palbociclib plus anastrozole administration for a given cycle, nivolumab must be omitted for that cycle. Participants who require a dose omission for nivolumab should be re-evaluated and resume treatment at the next cycle when re-treatment criteria are met.

Palbociclib can be interrupted, reduced, or discontinued both within a cycle and between cycles.

No dose modification for anastrozole is listed per full prescribing information.

Dose escalations (within subject) are not permitted for any study drugs.

Reason for dose modification will be retrieved from CRF dosing pages.

- The following parameters will be summarized by treatment group:
- Number of subjects with at least one dose modification (interrupted nivolumab dose, omitted nivolumab dose, interrupted palbociclib dose, reduced palbociclib dose).
- Number of nivolumab and/or palbociclib dose modifications per subject.
- Reason of nivolumab and/or palbociclib dose modification.

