### **7.6.8 Immune-Mediated Adverse Events (US Submission)**

IMAEs will be summarized by treatment group for each immune-mediated category / PT using the 100-day safety window:

- Overall summary of non-endocrine IMAEs by worst CTC grade (any grade, grade 3-4, grade 5) where immune modulating medication was initiated presented by Category / PT.
- Overall summary of endocrine IMAEs by worst CTC grade (any grade, grade 3-4, grade 5) presented by Category / PT.
- Overall summary of non-endocrine IMAEs leading to discontinuation by worst CTC grade (any grade, grade 3-4, grade 5) where immune modulating medication was initiated presented by Category / PT.
- Overall summary of endocrine IMAEs leading to discontinuation by worst CTC grade (any grade, grade 3-4, grade 5) presented by Category / PT.
- Overall summary of non-endocrine IMAEs leading to dose delay or reduction by worst CTC grade (any grade, grade 3-4, grade 5) where immune modulating medication was initiated presented by Category / PT
- Overall summary of endocrine IMAEs leading to dose delay or reduction by worst CTC grade (any grade, grade 3-4, grade 5) presented by Category / PT.
- Summaries of time-to onset and time-to resolution of non-endocrine IMAEs where immune modulating medication was initiated presented by Category.
- Summaries of time-to onset and time-to resolution of endocrine IMAEs presented by Category.

A by-subject listing of IMAEs will be provided. By-subject listings of time-to resolution for longest IMAEs cluster (any grade and grade 3-5 in separate summaries) will also be provided. For new studies which collect investigator assessment of potential IMAE data, a by-subject listing of AEs considered as immune-mediated events per investigator but not qualified for IMAEs definition will also be provided.

In addition, for all nivolumab treated subjects who experienced at least one IMAE, the following data presentation will be provided:

- Summary of subjects who were re-challenged with nivolumab by IMAE category, with extended follow-up.
- Summary of subjects who were re-challenged with nivolumab by IMAE category, with extended follow-up.

For these, re-challenge is considered to have occurred when last nivolumab infusion was administered after the onset of an IMAE.

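### The dose-modification AE tables select on 'delay/reduction', which matches at most two of the four dose-modification types that the SAP itself lists

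*SAP*

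**What the plan says.** SAP 7.6.5 plans two tables, one for all such AEs and one for the related ones, by system organ class, preferred term and worst grade, with a by-subject listing. The selection rule is that "AEs leading to dose delay/reduction will be summarized by treatment group". SAP 7.6.8 applies the same rule to immune-mediated events, for example "Overall summary of endocrine IMAEs leading to dose delay or reduction by worst CTC grade", with a matching table for non-endocrine events. SAP 7.10 puts the delay/reduction summaries, all and drug-related, into the package for choosing the dose of the Randomized Phase.

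The codes behind these tables are set out in SAP 7.1.1. Besides discontinuation and reduction it states "Adverse events that led to dose interruption of the drug will be coded with action" (interrupted) and "Adverse events that led to dose omission of the drug will be coded with action" (omitted). No code for delay appears.

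SAP 7.4.2 says what counts as a dose modification in the exposure summaries: "Number of subjects with at least one dose modification (interrupted nivolumab dose, omitted nivolumab dose, interrupted palbociclib dose, reduced palbociclib dose". It also says of nivolumab: "There will be no dose escalations or reductions of nivolumab allowed". The one sentence that links delay to a recorded action is in Protocol 9.2.9: "Please note that for this protocol, nivolumab delay means nivolumab omission".

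**The concern.** A table can be programmed only from values that exist in the data. Delay is not one of them, so the content of the 7.6.5 and 7.6.8 tables depends on how the programmer interprets the word, and two programmers could produce different tables from the same database. On the plain text, an AE that interrupted a nivolumab infusion or led to palbociclib being held is not selected, although SAP 7.4.2 calls both events dose modifications.

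Safety and tolerability of palbociclib plus anastrozole with or without nivolumab is a secondary objective (SAP 3.2), and these are the only tables that tie an AE term and grade to a change in dosing short of discontinuation. Protocol 5.1.2.1 says that expansion and de-escalation decisions in the run-in weigh AEs that are not DLTs, so an incomplete table would also reach that meeting.

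**Working it through.** No formula applies. The check sets the modification types of SAP 7.4.2 against the codes of SAP 7.1.1 and asks which ones the 7.6.5 wording selects.

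| Modification (SAP 7.4.2) | Code (SAP 7.1.1) | Selected, SAP text alone | Selected if Protocol 9.2.9 is applied |
|---|---|---|---|
| Palbociclib reduced | reduced | yes | yes |
| Nivolumab omitted | omitted | no | yes |
| Nivolumab interrupted | interrupted | no | no |
| Palbociclib interrupted | interrupted | no | no |
| Types covered | | 1 of 4 | 2 of 4 |

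**Reduction.** Nivolumab reductions are not allowed (SAP 7.4.2) and no modification is listed for anastrozole, so this half of the rule can select palbociclib only.

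**Delay.** Protocol 9.2.9 equates nivolumab delay with omission, and Protocol 7.4.4.1 fits this by sending the reader from the omission criteria to the delay criteria in Appendix 6. Neither place mentions interruption or palbociclib.

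**Can the unmatched types occur?** Yes. SAP 7.4.2.1 allows nivolumab infusions to be interrupted, and SAP 7.4.2 allows palbociclib to be interrupted within and between cycles. I assume that an AE with either consequence is recorded under the interrupted code.

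**Do other outputs supply the missing count?**

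- SAP 7.4.2 and 7.4.2.1 give the participants with modifications or infusion interruptions, the number per participant and the reasons, but no AE term or grade.
- The tables of SAP 7.6.6 give AEs by term and grade, but not by action taken with study drug.
- SAP 7.6.4 covers discontinuation only.

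No planned table therefore gives interruption-causing AEs by term and grade.

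**Scale.** The documents contain no interruption rates, so the undercount cannot be calculated. As a guide to leverage only, SAP 5 plans 3 to 6 run-in participants per dose level, so one participant missing from the table is 1/6 = 17% to 1/3 = 33% of a dose level.

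**The case against.** The best reply is that this is one undefined word and not an exclusion. Section 7.6.5 is titled for dose modification in general, SAP 7.4.2 lists the modifications, and a sensible programmer might map interrupted to delay. The data are also reported elsewhere. The 7.10 package contains the summaries of treatment modifications, the DLT summary and listing, and the AE listing, and the run-in follows 3 + 3 rules on DLTs. SAP 4.2.4 refers safety details to an IO Core SAP that is not among the documents and may define delay.

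Much of this stands. Nothing is lost from the database, nothing shows that the dose decision would be misled, and a definition in the IO Core SAP would reduce the repair to a cross-reference. It does not remove the mismatch: this SAP defines its codes, then selects on a term that is not among them.

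Two stronger readings are tempting, and the documents do not support them.

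- **That all nivolumab omissions are left out and only palbociclib reductions are counted.** This holds only if Protocol 9.2.9 is ignored. That sentence speaks for the protocol as a whole, and anyone who applies it would count omissions.
- **That Arms A and B would look closer to Arm C than they are.** Omissions are reachable as above, palbociclib interruptions can occur in all three arms, and there are no rates from which to infer a net direction. The study is also described as non-comparative.

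**Conclusion.** The concern holds as a mismatch between a selection rule and the coded data. As written, the dose-modification AE tables reach at most 2 of the SAP's own 4 modification types, and 1 of 4 if Protocol 9.2.9 is not carried into programming. Nivolumab infusion interruption and palbociclib interruption match nothing in either case.

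The effect is on completeness of reporting. The counts by system organ class, preferred term, grade and relatedness in 7.6.5 and 7.10, and by category, preferred term and grade in 7.6.8, would be incomplete or left to the programmer's choice. Its size is unknown and no direction of bias between arms is established. The conclusion assumes that the IO Core SAP does not already define delay in terms of the 7.1.1 codes, which cannot be checked from these documents. The change should be made before the tables are programmed.

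**What to change.** In SAP 7.6.5 (tables and listing), 7.6.8 and 7.10, replace delay/reduction with interruption, omission or reduction, and state that the events are selected by the three action codes of SAP 7.1.1. This brings the AE tables into line with the modification types in SAP 7.4.2. If the sponsor prefers to keep the word delay, it should be defined once in SAP 7.1.1 in terms of those codes and for each drug, with the Protocol 9.2.9 equivalence repeated there.

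The cost is a wording change and the matching table shells. No new data are needed, and only reporting changes; no dosing rule is touched.
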